3.1 Study design

This is a multicenter, open label trial to assess the safety, tolerability, pharmacokinetics and efficacy of inhaled QCC374 over a two year period, in subjects with PAH who have completed study QCC374X2201. This study will have two arms (Figure 3-1). In Arm 1, subjects randomized to active in the QCC374X2201 study will continue on QCC374 at their highest stable dose. In Arm 2, the subjects randomized to placebo in the QCC374X2201 study will complete a titration scheme similar to that of the active arm in QCC374X2201 protocol. For subjects in both Arms, the assessments obtained during the Day 111 visit for the companion QCC374X2201 study (including physical examination, vital signs, pulse oximetry, ECG, spirometry, 6MWD, **Corporate Confidential** and laboratory data) will be used as the baseline values for this study. **Information**

[figure not shown]
This study may be amended in the future to increase the treatment duration period, as additional data emerges for QCC374 in PAH.

Figure 3-1 QCC374X2201E1 Extension Study Design

Arm 1

Arm 2

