4.1 Inclusion criteria

Subjects eligible for inclusion in this study must fulfill **all** of the following criteria:

1. Written informed consent must be obtained before any assessment is performed.
2. Subject was enrolled in the QCC374X2201 study and completed per protocol.
3. For patients enrolling in Arm 2, the spirometry assessed at Visit 111 in the companion QCC374X2201 study must meet ATS criteria for acceptability and reproducibility. If necessary, this assessment can be repeated during the Screening Period.

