Physical examination		X			X			X			X			X	X
Pulse oximetry		X			X			X			X			X	X
Vital Signs		X			X			X			X			X	X
Pregnancy test		X ³			X ³			X ³			X ³			X ³	X ³
Body weight															X
Blood chemistry		X			X			X			X			X	X
Hematology		X			X			X			X			X	X
Urinalysis		X			X			X			X			X	X
Spirometry		X			X			X			X			X	X
ECG evaluation		X			X			X			X			X	X
6-Minute Walk Test		X			X			X			X			X	X
		X			X			X			X			X	
Corporate Confidential Information		X			X			X			X			X	
														X	
														X	
														X	
Echocardiogram															
Corporate Confidential Information								X							

Epoch	Extension-Treatment ^{8,9}															
Visit Name	Long Term Follow Up													EOS (30 days post last treatment visit)		
Visit Numbers ¹	419	420	421	422	423	424	425	426	427	428	429	430	431	432	433 ⁸	
Study Day(s)	330 ±5	360 ±5	390 ±5	420 ±5	450 ±5	480 ±5	510 ±5	540 ±5	570 ±5	600 ±5	630 ±5	660 ±5	690 ±5	720 ±5	750 ±5	
Time (post-dose)	-	-	-	-	-	-	-	-	-	-	-	-	-	-	-	
Drug dispensation	X	X	X	X	X	X	X	X	X	X	X	X	X	X		
Study drug administration	Study drug administration will be bid - refer to Section 3.1 and Site Operations Manual															
PK blood collection	See Table 8-3 below															
Concomitant medications	As required															
Adverse events	As required															
Serious adverse events	As required															
Comments	As required															
Study/epoch completion information															X	X

¹ Visit structure given for internal programming purpose only

² The earliest that informed consent can occur is Day 111 in the companion QCC374X2201 study, and informed consent can occur no later than 7 days after Day 111.

³ Urine Pregnancy Test (females only)

⁴ Spirometry assessment during screening is only required if the spirometry testing session for V111 in the QCC374X2201 study did not meet ATS criteria for acceptability and reproducibility.

⁵ Domiciling is optional. The subject should remain in the clinic until all assessments are complete.

⁶ Assessments to be completed immediately prior to first QCC374 administration.

⁷ Assessments to be repeated prior to dosing if more than 4 days have elapsed since the D111 QCC374X2201 assessments.

⁸ If a patient stops study medication prematurely, at a minimum, a safety evaluation must be completed. Then an attempt should be made to complete all assessments listed under Visit 433, with the investigator making the determination of what is safe and feasible to complete.

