1.4 Study design and treatment

This is a multicenter, open label trial to assess the safety, tolerability pharmacokinetics and efficacy of inhaled QCC374 over a two year period in patients with PAH who have completed study QCC374X2201. This study will have two arms. In Arm 1, patients who had been randomized to active in the QCC374X2201 study will continue on QCC374 at their highest stable dose. In Arm 2, the patients who had been randomized to placebo will complete a titration scheme similar to that of the active arm in QCC374X2201 protocol.

For both arms the study consists of a Day 1 visit, a treatment period of 720 days, and an EOS visit 30 days after treatment is completed. This study may be amended in the future to increase the treatment duration period, as additional data emerges for QCC374 in PAH.

All patients willing to participate in this trial will roll-over directly from the QCC374X2201 study after their 112 days of participation has been completed. The electrocardiogram (ECG), spirometry, 6MWD, **Corporate Confidential Data** hematology, blood chemistry, body measurement and urinalysis results from the QCC374X2201 Visit Day 112 visit will be used as the Day 1 assessments for the extension study.

Figure 1-1: QCC374X2201E1 extension study design**Arm 1: Subjects who completed QCC374X2201 and received QCC374****Arm 2: Subjects who completed QCC374X2201 and received placebo**

2 First interpretable results (FIR)

First interpretable results (FIR) will be provided for this trial.

The study FIR template (mock slides) can be found in CREDI in the study RAP folder.

The template shows the analysis / results to be presented in the FIR. Study outputs required to be created at the time of the FIR will be highlighted in TFL shells document and marked as “Key” in the Programming Deliverables Tracker (PDT) output list.

FIR will focus on the following analyses:

- Analysis populations (if needed)
- Subject disposition
- Demographics and baseline characteristics. Baseline characteristics will be presented both at Core (QCC374X2201) and Extension study (QCC374X2201E1) baseline (subject to data availability at baseline for each study) and will include, but are not limited to:
 - Etiology of PAH
 - Time from PAH diagnosis
 - PVR
 - WHO FC
 - Borg Dyspnea Score
 - NT-proBNP level
 - Background PAH therapy
 - Smoking status
 - FEV1% predicted
 - Lung volumes (TLC % predicted)

- DLco
- Historic right catheter vs catheter at baseline
- Safety results

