7.2 Descriptive analyses

Subject demographics and other baseline characteristics

All data for background and demographic variables will be listed by arm and subject. Baseline characteristics will be presented both at Core (QCC374X2201) and Extension study (QCC374X2201E1) baseline. The Extension baseline, is defined, as the Extension study screening visit where the respective measurements are available (as per the assessment schedule) and Day 112 of the Core study where they are not. Summary statistics will be provided by arm.

Relevant medical history, current medical conditions, results of laboratory screens, drug tests and any other relevant information will be listed by treatment group and subject.

Treatment

Data for study drug administration (rescue medication) and concomitant therapies will be listed by arm and subject.

Summary tables will be used to present the proportion of subjects who reached each QCC374 dose, the proportion of subjects who had their dose reduced due to an adverse event, and the proportion of subjects who completed 16 weeks of treatment by dose subject received most from Day 15 to Day 112. Summary statistics for the number of days at each dose will be provided.

Vital signs

All vital signs data will be listed by treatment, subject, and visit/time and if ranges are available abnormalities (and relevant orthostatic changes) will be flagged. Summary statistics will be provided by arm and visit/time.

ECG evaluations

All ECG data will be listed by treatment, subject and visit/time, abnormalities will be flagged. Summary statistics will be provided by arm and visit/time.

Clinical laboratory evaluations

All laboratory data will be listed by treatment, subject, and visit/time and if normal ranges are available abnormalities will be flagged. A separate listing is provided presenting all parameters in a subject with any abnormal values. Summary statistics will be provided by arm and visit/time.

Adverse events

All information obtained on adverse events will be displayed by arm and subject.

The number and percentage of subjects with adverse events will be tabulated by body system and preferred term with a breakdown by arm. A subject with multiple adverse events within a body system is only counted once towards the total of this body system and arm.

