For the legal requirements of ClinicalTrials.gov and EudraCT, two required tables on treatment emergent adverse events which are not serious adverse events with an incidence greater than 5% and on treatment emergent serious adverse events and SAE suspected to be related to study treatment will be provided by system organ class and preferred term on the safety set population.

If for a same patient, several consecutive AEs (irrespective of study treatment causality, seriousness and severity) occurred with the same SOC and PT:

- a single occurrence will be counted if there is ≤ 1 day gap between the end date of the preceding AE and the start date of the consecutive AE
- more than one occurrence will be counted if there is > 1 day gap between the end date of the preceding AE and the start date of the consecutive AE.

For occurrence, the presence of at least one SAE / SAE suspected to be related to study treatment / non SAE has to be checked in a block e.g., among AE's in a ≤ 1 day gap block, if at least one SAE is occurring, then one occurrence is calculated for that SAE.

The number of deaths resulting from SAEs suspected to be related to study treatment and SAEs irrespective of study treatment relationship will be provided by SOC and PT.

Other safety evaluations

Spirometry

All spirometry data will be listed by subject and visit/time. Summary statistics (raw values primarily, and change from baseline) will be provided by QCC374X2201 study arm and visit/time.

Baseline is defined as the Day 112 of the Core study for the subjects who received QCC374 in the Core study, and the Screening visit of the Extension study for the subjects who received placebo in the Core study.

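### The SAP takes the Arm 2 spirometry baseline from the Extension Screening visit with no fallback, but the protocol requires a Screening test only after a failed Core V111 session

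*SAP*

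**What the plan says.** **Baseline rule for spirometry.** SAP 7.2 (Other safety evaluations, Spirometry) plans summaries of raw values, which are primary, and of change from baseline, by arm and visit. The baseline is Core Day 112 for subjects previously on QCC374 "and the Screening visit of the Extension study for the subjects who received placebo in the Core study". No alternative is given for a missing Screening value.

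**When that measurement is taken.** Protocol Table 8-2, footnote 4, is conditional: "Spirometry assessment during screening is only required if the spirometry testing session for V111" fell short of the ATS quality criteria. Inclusion criterion 3 (Protocol 4.1) says that for Arm 2 "the spirometry assessed at Visit 111 in the companion QCC374X2201 study must meet ATS criteria for acceptability and reproducibility", with a repeat during Screening if necessary. The note at the end of Protocol 4.2 likewise treats the repeat as the exception.

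**Other statements of the baseline.**
- Protocol 3.1 covers both arms and includes spirometry among the Day 111 Core assessments that "will be used as the baseline values for this study". The synopsis also lists spirometry.
- SAP 1.4 includes spirometry among the assessments whose "results from the QCC374X2201 Visit Day 112 visit will be used as the Day 1 assessments for the extension study".
- SAP 7.2, under demographics and baseline characteristics, takes the Extension Screening visit "where the respective measurements are available (as per the assessment schedule) and Day 112 of the Core study where they are not".

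**The concern.** The SAP points to a measurement that the protocol asks for only when something has gone wrong. A subject whose V111 session was acceptable has met the spirometry criterion and need not be tested again at Screening. Under the spirometry paragraph that subject has no baseline and so no change value at any visit. Those who do have a baseline are mainly the subjects whose earlier session failed, a small group selected on test quality.

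All safety assessments belong to the primary objective. Protocol 3.5.3 names spirometry as the objective monitor for bronchospasm, and Protocol 7.2 makes clinically significant drug-related bronchospasm seen on spirometry a reason to stop treatment. Arm 2 is the group inhaling QCC374 for the first time, so its within-subject change, including change after the first dose, is the part of this summary that one would most want to be complete.

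**Working it through.** The plan gives no figure to reproduce. The check compares the texts and then sizes the result over a range.

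**Step 1. Is a value guaranteed at the visit the SAP names?** No. Footnote 4 requires it only after a failed V111 session.

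**Step 2. Does Day 1 supply another pre-dose value?** Not as the schedule reads.
- Footnote 6 marks the 0 m column: "Assessments to be completed immediately prior to first QCC374 administration". In the extracted table the Day 1 spirometry marks stand at 2 h and 4 h, not at 0 m.
- Footnote 7, "Assessments to be repeated prior to dosing if more than 4 days have elapsed since the D111 QCC374X2201 assessments", is attached to blood chemistry, hematology and urinalysis, not to spirometry.
- The table was read by machine, so column positions carry some doubt. The conflict does not depend on them, because the SAP names Screening rather than Day 1.

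**Step 3. Does another SAP rule override the spirometry paragraph?** None says that it does. The fallback in SAP 7.2 sits under baseline characteristics, and the spirometry paragraph then states its own narrower rule. SAP section 2 lists FEV1 % predicted among the baseline characteristics. Read literally, the same SAP could report an Extension-baseline FEV1 % predicted for an Arm 2 subject in one table and have no spirometry baseline for that subject in another.

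**Step 4. How many subjects?** Let f be the share of Arm 2 whose V111 session failed ATS criteria, and g the share of the others tested at Screening anyway.

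Share without a baseline = (1 − f)(1 − g), which is at most 1 − f (reached at g = 0).

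Neither f nor g is in the documents. Nor is the size of Arm 2: the synopsis expects about 30 Core completers and the allocation is not visible. Assume n = 10 or 15, g = 0, and X ~ Binomial(n, 1 − f) for the number without a baseline.

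| f (assumed) | 1 − f | Expected without baseline, n = 10 | P(X > n/2), n = 10 | Expected without baseline, n = 15 | P(X > n/2), n = 15 |
|---|---|---|---|---|---|
| 5% | 95% | 9.5 | 1.000 | 14.25 | 1.000 |
| 10% | 90% | 9.0 | 0.998 | 13.5 | 1.000 |
| 20% | 80% | 8.0 | 0.967 | 12.0 | 0.996 |
| 30% | 70% | 7.0 | 0.850 | 10.5 | 0.950 |
| 50% | 50% | 5.0 | 0.377 | 7.5 | 0.500 |

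With g = 0, more than half of Arm 2 is expected to lack a baseline for any f below 50%. Voluntary testing lowers this: at f = 10% and g = 10% the share is 0.9 × 0.9 = 81%.

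**Step 5. What does the corrected rule give?** Inclusion criterion 3 requires an acceptable V111 session or an acceptable repeat. Taking the repeat where done and V111 otherwise, every eligible Arm 2 subject has a baseline, and the share without one falls to about 0.

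**The case against.** The strongest reply is that this is a drafting slip whose intended reading is plain. The right fallback stands in the same SAP section, and it already covers FEV1 % predicted. Protocol 3.1, the synopsis and SAP 1.4 all point to the end-of-Core value. The analysis is descriptive, raw values come first, and Protocol 11.4.2 places end-of-Core assessments in the summary tables. Footnote 4 does not forbid a Screening test after an acceptable V111 session. The database might also carry the V111 value into the Screening visit, although no visible text says so.

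Most of this stands, and it limits the consequence. It does not make the stated rule correct. A specific definition normally governs over a general one placed under another topic, so someone programming from the spirometry paragraph would have no instruction to use the fallback.

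Three stronger readings are tempting, and the documents do not support them:
- *Within-subject change is lost for Arm 2.* It is not. The V111 values are collected and the change can be computed once the rule is corrected.
- *A post-dose Day 1 reading would become the baseline.* Nothing in either document directs this, and several statements point to the end-of-Core value.
- *The SAP's Day 112 is the wrong visit.* The protocol says Day 111 or V111 and the SAP says Day 112. The Core protocol is not available, so this may only be a labelling difference; in the extension, Visit 411 is Day 112.

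**Conclusion.** The Arm 2 spirometry baseline is wrong as written. It names a visit at which the measurement is conditional, gives no fallback, and disagrees with Protocol 3.1, SAP 1.4 and the fallback rule within SAP 7.2. These points rest on the text alone.

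The size rests on assumption. Up to 1 − f of Arm 2 would have no baseline, which is 70% to 95% if 5% to 30% of V111 sessions failed. It would be less than half only if about half or more of the sessions failed or many subjects were retested without need. A reader should not take it as established that most of Arm 2 will lack a baseline. What is established is that the rule allows this, and that the protocol treats a failed V111 session as the exception.

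The practical effect is limited to the change-from-baseline part of one descriptive safety summary. No hypothesis test is affected. The correction is still worth making, because it costs almost nothing and concerns first exposure to an inhaled drug with a recognised class risk of bronchospasm.

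**What to change.** In SAP 7.2 (Spirometry), replace the Arm 2 clause with: *for subjects who received placebo in the Core study, the Extension Screening session where a repeat was done, otherwise the end-of-Core visit (V111) spirometry.*

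With the same edit:
- Use one label for the end-of-Core visit throughout, after checking the Core visit schedule, so that Day 111, V111 and Day 112 cannot be taken for different visits. The Arm 1 rule needs no other change.
- Show the number of subjects with a baseline in each change table.

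The cost is one SAP clause, a label and a count, with no new data or visits. The small downside is that Arm 2 baselines come from two visits, about a week apart at most given the Screening window.

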7.3 Graphical presentation

Boxplots to visualize trends in longitudinal safety data (vitals, ECG, lab parameter) will be created. Mean (SD) plots will be used to visualize trends for spirometry.

Corporate Confidential Data
